## **1 SUMMARY**

### **1.1 Title**

Multicentric pilot study to compare the effectiveness of vaginal capsules with boric acid and *L. gasseri* and *L. rhamnosus* versus another drug with the same route of administration in patients with vulvovaginitis due to bacterial or candidal aetiology.

### **1.2 Protocol code**

EUDRACT Code: 2016-000371-24

Sponsor Code: DOBO-01-16

### **1.7 Ethical Review Committees (ERC)**

All the study materials have been reviewed and approved by:

- ERC of the Virgen Macarena-Virgen del Rocío University Hospitals (Seville) (rERC)
- Aragon ERC (*CEICA*)

The **Biomedical Research Ethics Coordinator Committee of Andalucía (CCEIBA)** will be the trial coordinator in Andalusia.

## 1.8 Study healthcare product and control treatment

- **Study healthcare product:** boric acid 150 mg, *Lactobacillus gasseri*, *Lactobacillus rhamnosus* and prebiotics.
- **Pharmaceutical form:** Capsule
- **Route of administration:** Vaginal
- **Therapeutic group:** D08AD. Antiseptics and disinfectants - Products with boric acid.
- **Control treatment (I):** Clotrimazole 100 mg (Gine-Canesten®).
  - **Pharmaceutical form:** Tablet
  - **Route of administration:** Vaginal
  - **Therapeutic group:** D01AC. Antifungal agents for topical dermatological use - Imidazole and triazole derivatives.
- **Control treatment (II):** Clindamycin 100 mg (Dalacin®)
  - **Pharmaceutical Form:** Suppository
  - **Route of administration:** Vaginal
  - **Therapeutic Group:** J01FF. Lincosamide macrolides and Streptogramins - Lincosamides.

## 1.9 Clinical trial phase

Postmarketing.

## 1.10 Objectives

### **Main:**

To assess the effectiveness of a vaginal application formula with boric acid and probiotics for the treatment of symptomatic episodes of vulvovaginitis (VV) against a control pharmacological treatment (according to the VV aetiology).

### **Secondary:**

- To determine the incidence of recurrence/relapse at 3 months.
- To assess the level of post-treatment vaginal flora restoration.
- To characterise the different symptomatic and microbiological profiles of vulvovaginitis.
- To assess the tolerance and safety of the product.

### **1.11 Study design**

Multicentric, Open, Prospective, Drug-controlled Randomised Clinical Trial.

### **1.12 Disease under study**

Infectious vulvovaginitis (including vulvovaginal candidiasis and bacterial vaginosis).

### **1.13 Type of study**

Clinical trial with healthcare products and pharmaceutical specialities. Pilot study.

### **1.14 Study population**

Women over 18 years of age who consult the gynaecologist due to suspicion of infectious vulvovaginitis.

### **1.15 Monitoring**

( [REDACTED] ) will be responsible for the logistics and monitoring of the study.

### **1.16 Treatment duration**

**Healthcare product subject to study:** 7 days

**Control drug (I):** 6 days

**Control drug (II):** 3 days

### **1.17 Expected clinical trial duration**

The planned duration for the recruitment of patients will be 4 months with a follow-up period of 3 months.

## **GLOSSARY OF ABBREVIATIONS**

AE	Adverse Event
BMI	Body Mass Index
BV	Bacterial vaginosis
CRF	Case Report Form
CRO	Clinical Research Organization
CT	Clinical Trial
ERC	Ethical Review Committee
GCP	Good Clinical Practice
IC	Informed Consent
ICH	International Conference on Harmonisation of Technical Requirements for Registration of Pharmaceuticals for Human Use
IS	Information Sheet
rERC	Reference Ethical Review Committee
SAE	Serious Adverse Event
STD	Sexually Transmitted Diseases
VAS	Visual Analogue Scale
VV	Vulvovaginitis
VVC	Vulvovaginal Candidiasis

## 2 INTRODUCTION AND JUSTIFICATION OF THE STUDY

Female lower genital tract infections are classified according to the primary location of signs and symptoms, theoretically distinguishing between vulvitis, vaginitis and endocervicitis. However, in practice, the inflammatory process is not usually limited to a single location, so in most patients it is manifested as vulvovaginitis (VV).

VV, which can affect both the vaginal mucosa and vulvar skin, is typically associated to symptoms and discomfort such as leukorrhea, itching, stinging, dysuria and, in some cases, dyspareunia. Most of these symptoms have an infectious origin, which is why their standardised approach involves the use of antifungal and/or antibiotic treatments.

According to different sources, VV represents more than one third of gynaecological consultations. Although most symptomatic episodes are effectively controlled with the different therapeutic alternatives available, the identification of pathogens resistant to the typically-used treatments raises the need to look for new alternatives.

It is estimated that 20-25% of VV are caused by different yeast species belonging to the *Candida sp* family, with the most frequent genus being *C. albicans* (more than 80% of cases). Furthermore, bacterial vaginosis (BV), which causes 40-50% of VV, is associated with different microorganisms such as *Gardnerella vaginalis*, *Mycoplasma*, *Bacteroides*, *Mobiluncus*, *Peptostreptococcus*, among others.

Most of these microorganisms are part of the vaginal flora without clinically manifesting themselves. Evidence suggests that a change in the flora's balance, particularly in the population of acidifying bacteria in the vaginal environment such as *Lactobacillus*, influences the growth of another type of microorganisms that finally cause the patient to become symptomatic.

Recurring forms, more typical in the case of candidiasis ( $\geq 4$  episodes/year), usually occur during the 3 months after treatment. The most accepted theory to explain this phenomenon is related to the persistence of the pathogen in the

vagina, corroborated by the isolation of forms with the same karyotype in recurrences.

Among the different treatment alternatives for infectious VV, the use of boric acid has been described as an effective, well-tolerated and particularly useful therapeutic option in the case of recurrent VV and candidiasis associated with non-albicans *Candida*. Most studies with vaginal boric acid have studied its administration at doses of 600 mg.

Boric acid is considered a topical action agent that, by combining its bacteriostatic, fungistatic and fungicidal properties, has shown effective results in the control of infectious VV symptoms. Although its mechanism of action is not clearly defined, a potential inhibitor effect of fungal oxidative metabolism that favours the properties previously described has been proposed.

In addition, many studies have been carried out in recent years that show positive results regarding the use of probiotics in patients with VV of infectious origin. The use of these products in the treatment of infectious VV is based on the role of *Lactobacillus* as bacterial flora, maintaining a vaginal pH that promotes balance in the vaginal microenvironment, controlling the growth of potential pathogens that cause VV and reducing the possibility of overcolonisation by *Candida*. There is little evidence available regarding the simultaneous use of antiseptics such as boric acid with probiotics to treat this type of patients.

*De Seta and col.* carried out a comparative study of conventional therapies for BV (Clindamycin) and VC (clotrimazole) and a combination of boric acid with probiotics (*Lactobacillus sp.*) in which a better concentration of lactobacilli was observed in the group treated with boric acid + probiotics 3 weeks after completing the treatment. These patients also registered a significant improvement in symptoms such as stinging, itching, the presence of leukorrhea and fetid vaginal discharge.

For all these reasons, the combination of boric acid with probiotics is postulated as a potential therapeutic alternative for the treatment of infectious VV, which

may end up being incorporated into the usual therapeutic arsenal against VV, and should therefore be compared to other current reference treatments in daily clinical practice.

### **3 OBJECTIVES OF THE STUDY**

#### **3.1 Main objective**

To assess the effectiveness of the vaginal capsule with boric acid and *L. gasseri* and *L. rhamnosus* for the treatment of symptomatic episodes of vulvovaginitis (VV) against a control pharmacological treatment (according to the VV aetiology).

#### **3.2 Secondary objectives**

- To determine the incidence of recurrence/relapse at 3 months.
- To assess the level of post-treatment vaginal flora restoration.
- To characterise the different symptomatic and microbiological profiles of VV.
- To assess the tolerance and safety of the product.

### **4 SOURCE OF INFORMATION**

The information will be obtained from the data collected during the patient's clinical visit, as well as from the data recorded by the patients and the self-administered scales of the Patient Questionnaires and Notebooks that will be handed to them by the investigators.

### **5 SCOPE OF THE STUDY**

Outpatient gynaecology and national emergency clinics.

### **6 STUDY DESIGN**

#### **6.1 Type of study**

Multicentric, open, prospective, drug-controlled, randomised pilot clinical trial in patients with vulvovaginitis of bacterial and candidal aetiology. Patients will be randomly assigned to two groups (healthcare product subject of study (boric

acid + *L. gasseri* and *L. rhamnosus*) or control treatment). The ratio will be 1:1 between the study product and the control treatment.

## **6.2 Study population**

### *6.2.1 Inclusion criteria*

- Women  $\geq$  18 years of age.
- Women with clinical manifestations of infectious VV.
- Women who agree to participate by signing the informed consent form.

### *6.2.2 Exclusion criteria*

- Symptoms (high suspicion) compatible with infection due to *Chlamydia trachomatis*, *Trichomona vaginalis*, *Neisseria gonorrhoeae* or *Herpes simplex*.
- Use of antifungal or probiotic agents during the last 2 weeks prior to the study.
- Patients who are receiving any other treatment with probiotics, vitamin complexes that may significantly interfere with the study assessments.
- Pregnant patients.
- Patients who may become pregnant (if there is a reasonable doubt about the possibility of pregnancy at the time of inclusion or during the study a blood pregnancy test will be performed to rule out this possibility).
- Patients who are menstruating at the time of inclusion.
- Breast-feeding patients.
- Immunocompromised patients.
- Patients who, based on the investigator's criteria, are not expected to complete the follow-up.

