#### 6.2.4 Discontinuation criteria

- Patients who, during the study period, receive/use some type of treatment and/or intervention (probiotics, vitamin complexes or vaginal showers) that may significantly interfere with the study assessments.
- Patients who, even while receiving the rescue treatment, show a lack of effectiveness\*. Patients who, after the baseline visit, are suspected to have an infection due to *Chlamydia trachomatis*, *Trichomona vaginalis*, *Neisseria gonorrhoeae* or *Herpes simplex*.

\*These patients will also be subject to follow-ups during the 3 months of study.

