## **6.6 Concomitant treatments**

The existence of concomitant treatments will be recorded. Only treatments that can influence the trial results will be reason for withdrawal of the product (*section 6.2.4*).

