### **8.2 Objectives of the study**

The analysis of the main objective will focus on the comparison of the effectiveness of the product under study (boric acid + *L. gasseri* and *L. rhamnosus*) and that of the control treatment with solid vaginal forms, according to the usual clinical practice (clotrimazole or clindamycin) and assessed according to the patient's clinical symptom scores (VAS, Sobel score) approximately 2 weeks after the end of the treatment. To do this, T tests for independent samples or non-parametric Mann–Whitney U tests will be used.

For the secondary objectives, the level of restoration of vaginal flora will be assessed by comparing the *Lactobacillus* count in baseline discharges and 2 weeks after treatment through T tests for related samples or non-parametric

Wilcoxon or McNemar tests. The incidence of recurrences/relapses at 3 months will be studied by means of proportion comparison tests (Pearson's chi-squared test). The characterisation of the different symptomatic and microbiological profiles of VV, as well as the tolerability, compliance and adverse events, will be analysed through descriptive statistics.

The possibility of carrying out additional analyses, depending on the results, with the relevant statistical tests in each case is not ruled out.

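### The pre-study exclusion covers recent antifungals and probiotics but not antibacterials, which leaves the paired before-after flora test open to counting spontaneous recovery as restoration

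*Combined protocol and SAP*

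**What the plan says.** The only pre-study washout is in section 6.2.2: "Use of antifungal or probiotic agents during the last 2 weeks prior to the study". The next criterion concerns current use and again names other products: "Patients who are receiving any other treatment with probiotics, vitamin complexes that may significantly interfere with the study assessments". Section 6.2.4 withdraws patients who "receive/use some type of treatment and/or intervention (probiotics, vitamin complexes or vaginal showers", but it applies during the study and not before it. Section 6.6 adds "The existence of concomitant treatments will be recorded", with no look-back period and no role in the analysis. Antibacterials are named in none of these.

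The trial takes both aetiologies (section 6.1), and the control for bacterial cases is vaginal clindamycin (section 6.4). As background, section 2 states "It is estimated that 20-25% of VV are caused by different yeast species" and refers to "bacterial vaginosis (BV), which causes 40-50% of VV".

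For the flora objective, section 8.2 compares the Lactobacillus "count in baseline discharges and 2 weeks after treatment through T tests for related samples", or a non-parametric equivalent. It describes no comparison between arms for this objective. The main analysis in the same section compares VAS and Sobel scores about two weeks after treatment between the randomised arms, with an independent-samples t test or Mann-Whitney test.

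**The concern.** The plan accepts that recent use of an active agent can spoil the baseline, but applies this to the candidal side only. A woman who used an antifungal last week is excluded; one who used an antibacterial last week may enter. No reason is given.

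This matters most for flora restoration, a secondary objective. Lactobacilli are bacteria, so a recent antibacterial can plausibly lower the V0 count. If the count then recovers unaided by V1, the paired test records a rise that the study treatment did not cause. This can happen in either arm, and randomisation cannot correct it because the test never contrasts the arms. The V0 culture, smear and pH can be affected in the same way.

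**Working it through.** **1. Is the gap closed elsewhere?** The places that could close it are the two product criteria in 6.2.2 (antifungals and probiotics in the past two weeks; probiotics and vitamin complexes now), 6.2.4 (on-study use only), 6.6 (recording only) and 8.2 (no adjustment, subgroup or sensitivity analysis for prior treatment). None does.

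**2. The plan's own figure.** Section 6.8 gives a minimum of 50 patients, and 6.1 gives 1:1 allocation, so 50/2 = 25 per arm. No alpha, power, effect size or SD is stated, so the 50 cannot be reproduced. It is used here only for n.

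**3. Flora test, illustration.** The following are assumptions, not figures from the documents: a share f = 10-20% of entrants are prior users; their count recovers by s = 1-2 log10 without treatment; the SD of change in non-users is 1 log10; there is no treatment effect and no other recovery; the paired t test is run in one arm of 25 at two-sided 5%.

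- Mean spurious change = f × s.
- SD of change in the mixture = √(1 + f(1 − f)s²).
- Rejection rates are from simulation.

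| f | s (log10) | f × s | SD of change | Rejection rate |
|---|---|---|---|---|
| 0 | – | 0 | 1.00 | 5% |
| 10% | 1 | 0.1 | 1.04 | 7% |
| 10% | 2 | 0.2 | 1.17 | 12% |
| 20% | 1 | 0.2 | 1.08 | 14% |
| 20% | 2 | 0.4 | 1.28 | 31% |

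If every patient is shifted by the mean and the total SD is held at 1, the rates for shifts of 0.1, 0.2 and 0.4 are 7.7%, 16.1% and 48.4%. The 48% ignores the variance that a mixture of users and non-users adds, so 31% is the matching figure.

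**4. Second set of assumptions.** With f = 10-30%, s = 0.5-1.0 SD of the count and a baseline-to-V1 correlation of 0.5, the spurious rise is 0.1 × 0.5 = 0.05 SD to 0.3 × 1.0 = 0.30 SD. The rejection rate runs from 5.7% to 25.4% (14.5% at f = 20%, s = 1).

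**5. Symptom comparison.** With the same f and s as in step 4 carried into V1 scores in both arms, the mean bias is about 0 and the type I error is 4.7-5.1%. Chance imbalance remains. The SD of the between-arm difference in prior use is √(2f(1 − f)/25), which is 8.5 percentage points at f = 10% and 13 at f = 30%. A gap of four or more prior users occurs in 10% to 28% of trials of this size.

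**6. Between-arm test of flora change.** Under the assumptions of step 3, a two-sample t test on the change in count rejects in about 5% of trials in all four scenarios. It removes the systematic error but not the added noise.

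**The case against.** The strongest reply has four parts.

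- **The size is assumed.** The documents give no frequency of prior antibacterial use, no effect on lactobacilli, no recovery rate and no SD. Even the direction is an inference. This stands: the result is a risk with an illustrative size.
- **The deeper flaw is the uncontrolled before-after test.** Any spontaneous recovery counts as restoration, with or without earlier antibiotics, so an exclusion alone does not make the test comparative. This also stands, and is why the fix includes a between-arm comparison. It does not remove the reason to protect the baseline.
- **Cost and size move together.** If 10-20% of candidates are prior users, that is 5-10 of 50 in a four-month recruitment period, and a broad population may be intended. This is fair and is stated as the cost.
- **Part of the record exists.** V0 takes clinical history, and concomitant treatments are noted. But without a defined look-back, prior use may not be captured consistently.

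A reader might infer that prior antibiotics bias the main result through a distorted change in symptoms. The documents do not support that: 8.2 compares post-treatment scores between randomised arms and specifies no change score. A reader might also take bacterial vaginosis to be the larger group in this trial. The percentages in section 2 are background epidemiology, and no enrolment split is planned.

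**Conclusion.** The omission is real, and no other section repairs it. Its systematic consequence is confined to within-patient before-after readings, chiefly the Lactobacillus test, with V0 culture, smear and pH open to the same problem. For the main comparison it means added noise and possible chance imbalance, not bias. Under the assumptions in step 3, the false restoration rate rises from 5% to about 7-31%; the second set of assumptions gives 5.7-25.4%. With few prior users or little unaided recovery, the effect is small. This is a worthwhile, inexpensive improvement to a secondary objective and does not invalidate the primary one.

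**What to change.** - In 6.2.2, add antibacterial agents (vaginal or systemic) to the existing pre-study exclusion. The window is a clinical decision for the sponsor to confirm.
- At V0, record prior antibacterial use with a defined look-back.
- In 8.2, report the flora results with and without any such patients, and add a between-arm comparison of the change in Lactobacillus count.

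The cost is a few words in the criterion, one case report form item and two short additions to the analysis. Some candidates will be lost or deferred: up to the assumed 10-20%, which is 0.10 × 50 = 5 to 0.20 × 50 = 10 of the minimum sample, and fewer if prior use is rarer.

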### *6.2.3 Rescue criteria*

In cases where the patient requires "rescue treatment", the treatments will be crossed. In the event of changing treatment group (crossover), the patient will be considered to be back at V0 and the tests/examinations corresponding to the baseline visit will be repeated.

The patient will change group to receive alternative treatment in the following cases:

- Patient with hypersensitivity to the first assigned treatment.
- Worsening of symptoms within 3-4 days of starting the assigned treatment.
- Evidence or indications of lack of effectiveness after the first assigned treatment.
- Patient who demonstrates a willingness to change treatment.
- In cases where the perceived lack of effectiveness is associated with a suspected mixed aetiology infection (candidal and bacterial):
  - If they are in the control group, they will be changed to the treatment under study (boric acid + *L. gasseri* and *L. rhamnosus*).
  - If they are in the study group, they will be changed to the antifungal treatment (Gine-Canesten®; Clotrimazole 100 mg). If this treatment fails, BV will be treated with antibiotic treatment (Dalacin®; Clindamycin 100 mg).

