### 6.3.3 Baseline Visit – $V_0$ (inclusion)

After the case history and initial examination, which will serve to substantiate the suspicion of VV due to infection, patients will be recommended to participate in the trial provided they meet the inclusion/exclusion criteria. Once the patient Information Sheet (PIS) has been handed over, the patient has signed the Informed Consent (IC) form and the investigator has verified that the patient meets the inclusion and exclusion criteria, they will proceed to fill in the CRF baseline visit sections.

During this first visit, socio-demographic data, relevant clinical history and gynaecological history will be recorded. The investigator will assess the patient's symptoms by recording the presence of clinical signs and symptoms of infectious VV (stinging, itching, erythema, oedema, abnormal vaginal discharge, etc.) and the *Sobel score* (see section 7.0). The vaginal pH determination test will then be carried out and the samples for the different laboratory tests will be collected, which will consist of: spreading the vaginal discharge sample on a slide to subsequently count the *Lactobacillus spp.* and collecting the discharge sample with a swab that will also be used for the diagnostic confirmation culture and for the fresh vaginal smear. The samples will be stored properly according to the instructions specified in the manual of use of the sampling kit until the samples are collected.

The patient will be given the treatment corresponding to the code assigned to her, reminding her that she has the possibility of changing treatment group, at the time that she deems appropriate. If the assigned treatment is ineffective or

is not tolerable, the patient may contact the hospital to bring the first control visit forward and request a change of treatment.

During the baseline visit, the patient will be given a CRF which she must fill in and return at the end of the visit and a card with a link to the online home CRF (Patient diary) that must be filled in over the course of the study. The home CRF will be used to monitor the patient during the follow-up weeks. The home CRF may also be delivered on paper and the patient must deliver it later.

The investigator will give the patient product for one treatment cycle (which may range from 3 days (Clindamycin) to 7 days (boric acid 150 mg, *L. gasseri*, *L. rhamnosus*)).

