The patient must return the empty blisters and/or surplus product during the first control visit. One week after the baseline visit, the patient will be contacted by telephone to find out her condition and if she is responding to the treatment, to assess the need for a rescue treatment or to arrange the first control visit. The first in-person control visit ( $V_1$ ) will be carried out at least 2 weeks after the treatment has been completed.

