#### 6.3.4 Control telephone contact a week after starting the treatment:

The investigator will contact the patient and will proceed with a brief questionnaire to decide whether the patient responds correctly to therapy depending on the symptoms the patient will describe and their severity. The different options in this scenario are:

Patient condition	Investigator's action
Disappearance of symptoms	In-person appointment ( $V_1$ ) within two weeks of the telephone contact and the end of the treatment (21 days from $V_0$ ).
Improvement of symptoms, but the patient still has mild clinical signs and symptoms	In-person appointment ( $V_1$ ) within two weeks of the telephone contact and the end of the treatment (21 days from $V_0$ ); we recommend that she request an appointment if there is no improvement in the following days. If there is a suspicion that there is still an

	infection, rescue treatment will be recommended.
Deterioration/Lack of effectiveness	The patient must arrange an appointment as soon as possible to proceed with the alternative rescue treatment.

Depending on the investigator's criteria, an appointment will be made with the patient for an in-person visit. When making an in-person appointment, the investigator will take into account the date of the patient's last menstruation to prevent it from coinciding with the patient's 1st control visit. To this end, the investigator may slightly extend the 2-week margin previously established between the call and the control visit.

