#### 6.3.5 1st Control Visit ( $V_1$ )

The second in-person visit of the study will be carried out approximately two weeks after completing the treatment.

As with  $V_0$ , the investigator and the patient will have a CRF that they must fill in. The investigator will record the data regarding the clinical examination and repeat the tests and collect the samples corresponding to  $V_1$ . The results of the analytical tests carried out during  $V_0$  will also be recorded.

The patient will fill in the corresponding CRF and return it at the end of the visit. An approximate time and date will be specified for the follow-up telephone interview around 2 months after the inclusion and an appointment will be made for the final follow-up visit (3 months from the patient's inclusion in the study).

If the investigator suspects a potential lack of effectiveness of the assigned treatment, rescue with the other therapeutic alternative of the study may be suggested according to the aetiology of the VV. In the event of crossing treatments, this visit will be considered the new baseline visit ( $V_0$ ), for the purpose of collecting data and samples. The same procedure will be followed if the second visit is brought forward at the patient's request.

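### After a crossover, no rule ties the group comparison to the randomised arm and first course, and patients who cross before V1 have no unrescued score at the 2-week point

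*Combined protocol and SAP*

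**What the plan says.** **Crossing and the reset.** Section 6.2.3 introduces its list of reasons with "The patient will change group to receive alternative treatment in the following cases". It adds: "In the event of changing treatment group (crossover), the patient will be considered to be back at" V0, with the baseline tests repeated. Section 6.3.5 says of a crossover at V1: "In the event of crossing treatments, this visit will be considered the new baseline visit". It limits this to the collection of data and samples, and applies the same procedure to a visit brought forward at the patient's request. Section 6.2.3 does not state that limit.

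**When crossing can happen.**
- During the first course, under 6.2.3: "Worsening of symptoms within 3-4 days of starting the assigned treatment".
- On preference, with no time condition, also under 6.2.3: "Patient who demonstrates a willingness to change treatment".
- At a visit brought forward for an ineffective or poorly tolerated treatment, under 6.3.3: "the patient may contact the hospital to bring the first control visit forward and request a change of treatment".
- After the week-1 call, for deterioration or lack of effect, under 6.3.4: "The patient must arrange an appointment as soon as possible to proceed with the alternative rescue treatment".

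**When V1 falls.** Section 6.3.3 says it "will be carried out at least 2 weeks after the treatment has been completed". Section 6.3.4 gives 21 days from V0, which may be extended slightly to avoid menstruation. Section 6.3.5 says about two weeks after treatment.

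**The analysis.** Section 7.3 counts patients with resolved symptoms per group two weeks after treatment, and lists rescue success as a separate end point. Section 8.2 compares VAS and Sobel scores between groups at about that time, by t test or Mann-Whitney. Neither section defines an analysis population, says which course is meant, or covers rescued patients or missing scores.

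**The concern.** The protocol changes a crossing patient's group and resets her baseline, while the analysis sections refer only to groups and to treatment. If the reset carries through, a first-course failure could be scored after taking the other arm's product, counted in the other arm, or left out. Three of the five reasons in 6.2.3 are worsening or lack of effectiveness (one of them tied to suspected mixed infection), so crossing depends on the outcome being compared. The trial is open, and 8.2 leaves room for further analyses depending on the results. Without a rule, the choice would be made with outcomes by arm in view.

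The main risk is a distorted estimate. Scoring after rescue pulls the arms together, and the result can be mistaken for similar effectiveness.

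**Working it through.** **Step 1: which patients lack a first-course score at the 2-week point.** Course lengths in 1.16 are 7 days (study product), 6 (clotrimazole) and 3 (clindamycin). Two weeks after the scheduled end is therefore day 7 + 14 = 21, 6 + 14 = 20 or 3 + 14 = 17 from V0. Crossing on early worsening (days 3-4), after the week-1 call (about day 7) or at a visit brought forward ahead of that point comes before it. Any score from those patients at the 2-week point is a post-rescue score. What they do have is the examination at crossover, because 6.2.3 repeats the baseline tests. A patient who crosses at the scheduled V1 has been examined there before rescue, so her first-course score exists.

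**Step 2: size.** The plan has no figure to reproduce: 6.8 gives a minimum of 50 patients without a derivation, and no resolution or crossover rate appears anywhere. All rates below are assumed.

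- a = 0.80: first-course resolution, control. b = 0.50: study product. Difference 30 points.
- c = 0.25 or 0.50: share of failures who cross.
- e: share of crossers affected by the handling in question. e = 0.5 means half cross early and the others' first-course V1 score is kept. e = 1 means all are affected.
- Each product works as well in rescue as first line. The arms are of equal size. k = c × e.

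*Scored after rescue, in the randomised arm:*
[a + k(1 − a)b] − [b + k(1 − b)a] = (a − b)(1 − k)
- e = 0.5, k = 0.125: 0.8125 − 0.5500 = 0.2625
- e = 0.5, k = 0.25: 0.825 − 0.600 = 0.225
- e = 1, k = 0.25: 0.825 − 0.600 = 0.225
- e = 1, k = 0.50: 0.850 − 0.700 = 0.150

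*Early crossers dropped:* a/(1 − k(1 − a)) − b/(1 − k(1 − b))
- k = 0.125: 0.8205 − 0.5333 = 0.287
- k = 0.25: 0.8421 − 0.5714 = 0.271

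*Early crossers counted in the other arm:* (a + k(1 − b)a)/(1 − k(1 − a) + k(1 − b)) − (b + k(1 − a)b)/(1 − k(1 − b) + k(1 − a))
- k = 0.125: 0.85/1.0375 − 0.5125/0.9625 = 0.8193 − 0.5325 = 0.287
- k = 0.25: 0.90/1.075 − 0.525/0.925 = 0.8372 − 0.5676 = 0.270

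| Handling | 25% of failures cross | 50% cross |
|---|---|---|
| Randomised arm, first course, early crossers not resolved | 30 | 30 |
| Half cross early, dropped | 28.7 | 27.1 |
| Half cross early, counted in the other arm | 28.7 | 27.0 |
| Half cross early, scored after rescue | 26.25 | 22.5 |
| Extreme: all crossers scored after rescue | 22.5 | 15 |

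For a 20-point difference (80% v 60%), scoring the early half after rescue gives 0.20 × 0.875 = 17.5 or 0.20 × 0.75 = 15 points.

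**Step 3: the score scale of 8.2.** Suppose the four Sobel items (0 to 3 each) are summed to 0-12, with assumed means of 0.6 if resolved and 6.0 if not. Mean differences are then 5.4 times those above: 5.4 × 0.30 = 1.62 becomes 5.4 × 0.2625 = 1.42 or 5.4 × 0.225 = 1.22. This rescales the same illustration and is not separate evidence. VAS is not quantified.

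**The case against.** The case against is substantial. Section 6.3.5 confines the new baseline to data and sample collection, and 6.2.3 itself ties the return to V0 to repeating tests. The protocol calls the first course the assigned treatment and the second one rescue, and rescue success has its own end point. The natural reading of 7.3 and 8.2 is then the first course by randomised group. This is also a pilot with no power claim.

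Most of that stands for patients who cross at the scheduled V1. It does not supply a score for those who cross earlier, and no sentence turns the favourable reading into an analysis rule. The pilot label removes any complaint about power, but 8.2 still plans a between-group test.

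Three stronger readings are tempting and unsupported:
- *The plan directs analysis in the arm crossed to.* It does not. The group-change wording in 6.2.3 permits that reading, but 7.3 and 8.2 do not adopt it.
- *The effect would shrink to 22.5 or 15 points.* That needs every crosser to cross early, or existing V1 scores to be discarded.
- *The 3-month clock restarts.* Sections 6.3.2 and 6.3.5 and the heading of 6.3.6 count from inclusion. The references to the baseline visit in the text of 6.3.6 and 6.3.7 need only an editorial match.

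Comparing randomised arms with rescue included is also legitimate, but it answers a different question.

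**Conclusion.** The point holds in two parts of unequal strength. The firm gap is the early crossers: they have no unrescued 2-week score on any reading, and nothing says how they enter the main comparison. The lesser gap is that 7.3 and 8.2 do not name the randomised arm and first course, although 6.3.5 and the separate rescue end point favour them for crossers at the scheduled V1.

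In the illustration, the loss from a 30-point difference is 3.75 or 7.5 points if early crossers are scored after rescue, and about 1.3 or 2.9 if they are dropped. These sizes depend wholly on the assumed rates and on half of crossers crossing early. What does not depend on them is the direction of post-rescue scoring under equal efficacy in rescue: the difference shrinks by the factor 1 − k, whichever arm is better. Because the trial is open, the rule must be written before data are seen.

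**What to change.** Leave the clinical rescue rule unchanged.

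1. In 6.2.3, state as 6.3.5 does that the return to V0 is for data collection only.
2. In 7.3 and 8.2, state that group comparisons are by randomised arm with the original V0 and first-course data, and that restarted courses are reported only under rescue success.
3. Reconcile the V1 timing in 6.3.3, 6.3.4 and 6.3.5 into one cut-off counted from the scheduled end of the first course. A patient who crosses at or after that V1 keeps her pre-rescue V1 score, and no later visit replaces it. A patient who crosses before it stays in her randomised arm and counts as not resolved. For Sobel and VAS, name one rule in advance, for example worst rank with Mann-Whitney or the pre-rescue score at the crossing visit, and report the other as a sensitivity analysis. Which of the two leads is a choice; naming it beforehand is the requirement. Add a sensitivity analysis that classifies preference and hypersensitivity switches by symptom status before the switch.
4. For 3-month recurrence, keep crossers in their randomised arm, count from inclusion, and show first-course failure or rescue as its own category beside recurrence. Post-rescue follow-up is then not read as first-course success.
5. For *Lactobacillus*, pair the original V0 with the first-course post-treatment sample, report how many early crossers are left out, and include their pre-rescue sample in a sensitivity analysis.

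**Cost.** A few sentences in 6.2.3, 6.3.3 to 6.3.5, 7.3 and 8.2, plus a CRF field for date and reason of crossover if none exists. No extra visit or sample is needed, since 6.2.3 already repeats the tests.

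**Downsides.** Reported success falls: with 50% of failures crossing, all early, 85% v 70% becomes 80% v 50%. Counting preference switches as failures can also create a difference. With 70% true resolution in both arms and 10% of study-arm resolvers switching early by preference, the study arm shows 0.70 × 0.90 = 63% against 70%. The sensitivity analysis in item 3 is there for this reason.
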